3.3.2 Laboratory Tests

[figure not shown]
Laboratory tests will be performed as judged appropriate by the treating physician. This study does not require additional laboratory tests to be performed. The laboratory test results of interest will be registered if available.

⁶ It is recommended to repeat bone marrow assessments (at the first follow-up visit) to confirm MDS diagnosis.

4. Organization and Responsibilities

4.1 Overall organization

The European MDS Registry is an initiative of the European LeukemiaNet MDS Work Package. The registry is built as a central international platform for registration of data collected by centres (referral sites) sometimes in the context of their local/national registries. The collection of data is coordinated by the operational team consisting of representatives from all countries involved. The central organization is responsible for the management of data and a central unit involved in the statistical analysis. An organisational structure, schematically represented below, has been designed for effective management of the EUMDS Registry.

4.2 Steering committee

The steering committee (SC) is the ultimate decision-making body of the registry and consists of (one or more) representatives from all participating countries, the Chief Investigator (voting members), the project manager, and a representative from the Central Data Management and Statistic Unit (non-voting members). The number of representatives per country will be based on the proportion of patients recruited in the Registry according to the Election policy as approved by the SC.

The SC is responsible for the general design (i.e. study protocol, CRFs), conduct, and overall progress of the Registry. The SC selects the sites for participation in the registry and monitors the availability of resources at all sites. The patient inclusion rate is monitored during the enrolment period of the study. Proposed research questions (sub studies) as well as statistical analysis plans have to be approved by the steering committee. Finally, the SC takes decisions concerning publication policy and authorship.

The SC is supported by **Project Management** and an **Executive Committee**. Project management is responsible for the general day-to-day coordination and execution of general tasks of the Registry (i.e. administrative, financial, contractual, newsletters). The Executive Committee (consisting of the Chief Investigator, 4-6 country representatives, the project manager, and a representative from the Central Data Management and Statistic Unit) is responsible for the day-to-day management of the Registry, and to advice / prepare proposals for the SC. Members of the Executive Committee are appointed according to the Election policy as approved by the SC.

During the inclusion period, the SC will meet every 6 months in a plenary session and by intercurrent TC if necessary. During the follow-up phase of the study, meetings will take place at least once a year in a plenary session. The secretary of the SC will be responsible for drafting the minutes of each meeting and circulating this document after approval.

4.3 Operational Team

The operational team (OT) is chaired by the project manager from the sponsor institution. The OT consists of the coordinators from the referral sites, representatives from the Central Data Management and Statistic Unit, an administrator for the regulatory issues and archive (non-voting member).

The OT is responsible for the overall coordination of the project in the participating countries. This includes the arrangement of support for the contract duties, the distribution of sites metrics, such as the number of patients included, coordination of the referral sites and the organization of Site Training. The project manager organizes all meetings, prepares and distributes the agenda and minutes. Finally, the project manager supports the preparation of publications.

The OT will meet every 12 months in a plenary session (during and after completion of recruitment) and TC will be scheduled on demand. The project manager is responsible for the preparation of the minutes of each meeting and circulation of this document. It is the duty of the project manager to report the important issues to the members of the SC.

4.4 Central Data Management and Statistic Centre

The Central Data Management and Statistics Centre is responsible for the design and maintenance of the core database, data transfer algorithms, and the EUMDS website (www.eumds.org), which will be part of the European MDS competence network website (www.mds-europe.eu). The data management centre prepares working instructions related to the data entry and cleaning, executes the data cleaning and provides a database lock. The statistics centre prepares and executes the statistical analysis. It provides statistical support during the preparation of publications and provides metrics by site.

5. Statistics

The Central Statistical Unit is responsible for the development of the details of the statistical analysis plan. The detailed statistical analysis plan has to be approved by the Steering Committee. This also applies whenever changes in the analysis plan are being considered.

5.1 Sample size

This study is exploratory in nature. Thus, the estimated sample size is not based on a statistical hypothesis, but on an estimation of the number of patients who are diagnosed with MDS per centre in an observation period and sufficiently large to perform some subgroup analyses.

5.2 Collection of clinical variables

All data collected for each patient are displayed in the patient data listings. Unless otherwise stated, *baseline* is defined as the first observation at the time of diagnosis. The tabulation of laboratory data, vital signs and LVEF indicate the normal ranges for each variable. Each value is classified as falling above, below or within normal limit. It is impossible to use a single central laboratory for all parameters and all patients. However, to avoid the issue of collecting hundreds of normal ranges, standard normal ranges will be defined and applied for the purpose of statistical analysis.

5.3 Demographics and disease management

Descriptive analyses will be undertaken at the end of the follow-up period using standard statistical methods to examine the subjects' demographics, disease characteristics and management of these disorders. Interim analyses are described in 5.5.

Time-to-event analyses, namely Kaplan-Meier and Cox proportional hazard regression will be used to estimate progression-free and overall survival:

- **The proportion (with 95% CI) of patients that has progressed to higher risk MDS and/or leukaemia.** The median, range and 95% CI for time to progression will be calculated. Time to progression is defined as the time from diagnosis to the date of the first objective progression to a higher stage of MDS or to leukaemia or the last date the patient was assessed and found to be progression-free. Patients who have been lost to follow-up or have died from any cause (including non disease-related deaths) without documentation of progression will be censored at the last date they were assessed and found to be progression-free. Patients who have not progressed or died will be censored at the last date they were found to be progression-free.
- **The proportion (with 95% CI) of patients that has died during follow-up.** The median, range and 95% CI for survival will be calculated. Overall survival is calculated for all patients from the date of MDS diagnosis to the date of death from any cause. Patients with no documented death are censored at the last date they were known to be alive.
- The proportion (with 95% CI) of patients that experiences an event (e.g. iron overload, cardiac failure, renal failure and/or other co-morbidities).

- The median, range and 95% CI for time to development of an event. Time to the initiation of treatment aimed at the event.
- The proportion (with 95% CI) of patients treated with any treatment for MDS recorded in the registry (including type, dose and schedule of treatment).

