1.2 Classification

Classification systems have been developed to serve as a guide for the diagnosis, estimation of prognosis and management of patients with this disease. However, newly acquired knowledge about the pathogenesis of MDS and the development of novel forms of therapy require that classification systems are continuously open to changes. From 1982 up until 1997, the myelodysplastic syndromes have been classified according to the FAB (French-American-British)-criteria.[5, 6] In this classification five subcategories have been described, based on the percentage of blast cells in blood and bone marrow, the percentage of ring sideroblasts and the number of monocytes: refractory anaemia (RA), refractory anaemia with ring sideroblasts (RARS), refractory anaemia with excess blasts (RAEB), refractory anaemia with excess blasts in transformation (RAEB-t) and chronic myelomonocytic leukaemia (CMML). Advanced MDS is defined as RAEB with more than 10% blast cells and RAEB-t. Median survival of these patients is generally shorter than 12 months. Because of the limitations of the FAB classification, the World Health Organization (WHO) [7] has provided a new system that classifies patients according to the number of cell lineages affected, the number of blasts in peripheral blood and bone marrow, the presence of ringed sideroblasts and the result of cytogenetic analysis. Patients with RA (+/-RS), RCMD (+/-RS), or a solitary deletion of the long arm of chromosome 5, have a relatively good prognosis regarding survival and risk of developing AML. Prognosis is worse in the RAEB-1 subgroup. Patients with RAEB-2 in general have the highest risk of progression to AML and the lowest overall survival. One of the major changes in the WHO classification compared to the FAB classification is lowering the blast percentage for the diagnosis of AML

from 30% to 20%. Several studies have suggested that there is little difference between RAEB-t and AML in terms of prognosis and response to chemotherapy. As a consequence RAEB-t has been eliminated from the MDS classification and included in the AML diagnosis.[7]

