3.1 Overall Study Design

The registry is designed to collect information about a large cohort of newly diagnosed MDS patients from clinical centres within the participating European countries. Patients will be observed until death or until termination of the EUMDS Registry (up to 12 years after enrolment or longer if the study is extended).

- *Enrolment:* each centre should register all consecutive eligible patients who present during the enrolment period, or until the achievement of the study recruitment target. Patients can be included up to 100 days after diagnosis.
- *Follow-up:* follow-up visits will be scheduled according to the standard practice of the centre and to the treating physician's best judgment. Reports of the follow-up visits will be collected every six months. Clinical and laboratory evaluations for disease or treatment monitoring may be performed more often in dedicated studies running in the centres, but the EUMDS Registry will only collect data at 6 months intervals.

In this study, no clinical, instrumental, laboratory assessments, or therapeutic intervention will be performed other than those required for disease management according to local best practice. The only exceptions will be the Patient Reported Outcomes (PRO) questionnaires and blood sample collection for biological correlative studies, including molecular data. In selected countries and centres, ancillary HRQoL, cardiac function and pharmaco-economics sub-projects will be launched to collect information about the HRQoL of patients and cost implications of the therapeutic strategies (separate protocols).

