3.2.2 Inclusion Criteria

Patients must meet all of the following criteria to be included in the European MDS Registry:

- Age \geq 18 years
- Newly diagnosed patient (within 100 days from the date of the diagnostic BM aspirate)
- MDS classified according to current WHO criteria (both 2008 [8] and 2016 [10] will be recorded)³
 - All sub groups of MDS

- Therapy-related MDS
 - MDS with Fibrosis (MDS-F)
 - AML with 20-30 percent marrow blasts (former RAEB-t)
 - CMML and other forms of mixed MDS/MPD
- IPSS and IPSS-R Risk group classification (*mandatory*)⁴
 - Able and willing to provide the written informed consent

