- Concomitant diseases, including but not limited to cardiac insufficiency, ophthalmic conditions including lens opacities and cataract, hearing impairment, diabetes mellitus, endocrine dysfunctions, renal or liver disease
- All concomitant medication
- Laboratory values:
 - Peripheral blood: Hb concentration, white cell count, neutrophil, lymphocyte, monocyte, eosinophil and basophil count, platelet count, MCV, CRP, reticulocytes, glucose, albumin, LDH, liver transaminases, ferritin, erythropoietin, transferrin saturation level, serum creatinine and calculated creatinine clearance
 - Bone marrow: date of BM aspirate and/or biopsy, percentage of blasts, percentage of ring sideroblasts, cytogenetics (karyotype)⁴
 - Urine: urinalysis for protein (by dipstick)
- Samples for biological correlative studies, including molecular studies:

*For all **new included** patients*

 - 2 x EDTA-blood tubes (each 7 ml) for molecular analyses **at screening** (see appendix A7.A for handling of samples).
 - *If EDTA-blood is not feasible*: BM aspirate 3-5 ml, or Isolated DNA 2-5 µg of **screening visit** (preferred) or at least collected within +/- 3 months before or after diagnosis. Only in the cases that 'patients are not treated' or 'patients are only treated with EPO', samples within +/- 6 months before or after diagnosis (see appendix A7.B for specifications per sample type).

Samples will be labelled only with EUMDS ID and date and time of sampling. *Collected samples for molecular analyses will be stored in the central tissue bank of the EUMDS Registry or can be stored in a local or in a national biobank if available.*

- **Optional:** Extra serum sampling only at screening for future research (see appendix A7.C for handling of samples)⁵

For **already included** patients (if (re-)consent is adequate):

- Isolated DNA 2-5 µg, viable cells/cell pellets, cytogenetic pellets, or (1-)3 unstained (or stained) BM smears of **screening visit** (preferred) or at least collected within +/- 3 months before or after diagnosis. Only in the cases that 'patients are not treated' or 'patients are only treated with EPO', samples within +/- 6 months before or after diagnosis (see appendix A7.A/B for handling of samples).
- Flow cytometry (FCM): performed yes/no, if performed according to the ELN FCM WP8 platform: diagnosis (see appendix A6)

3.3.1.2 At each follow-up visit, including end of study:

Follow-up data will be reported at 6-monthly intervals for all registered patients.

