8.2 Informed Consent

All patients who are eligible for inclusion are informed of the aims and nature of the study. They are informed that all their clinical data will be treated confidentially, but that their medical records may be reviewed by authorized persons other than their treating physician for study purposes.

All patients will be informed that participation is voluntary and that they can refuse participation at any time, without consequences for their further treatment. Documented informed consent will be obtained for all patients before they are registered. The informed consent procedure will be conform to the ICH guidelines on Good Clinical Practice (ICH-GCP) and will be in accordance with national and local regulatory requirements.

Human tissues collected in the context of this registration project will be used for scientific studies and genetic characteristics that play a role in MDS. Informed consent must be obtained for collection or 'further use' and storage of human tissues for ongoing or future research. The treating physician may inform the patient about new relevant information from this research which will affect their personal outcome in relation to their MDS. To ensure anonymity, all samples will be coded by the provider (or their staff) prior to transfer to the researcher.

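### Overall survival is counted from diagnosis, but patients enter only when alive and consented up to 100 days later; without delayed entry, absolute early survival is overstated

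*Protocol*

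**What the plan says.** **Time origin and estimators (Protocol 5.3).** "Overall survival is calculated for all patients from the date of MDS diagnosis to the date of death from any cause". For progression: "Time to progression is defined as the time from diagnosis to the date of the first objective progression". The methods are named: "Time-to-event analyses, namely Kaplan-Meier and Cox proportional hazard regression will be used to estimate progression-free and overall survival".

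**Entry (Protocol 3.1 and 3.2.2).** "Patients can be included up to 100 days after diagnosis"; the inclusion criterion reads "Newly diagnosed patient (within 100 days from the date of the diagnostic BM aspirate".

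**Consent (Protocol 8.2).** "Documented informed consent will be obtained for all patients before they are registered". Section 3.2.3 excludes anyone unable to consent.

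**Dates.** Section 3.3.1.1 collects both the date of diagnosis and the date of inclusion.

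No section mentions delayed entry, left truncation, a risk set that starts at registration, or a landmark.

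**The concern.** Registration requires a living patient who can consent. Someone who dies between diagnosis and registration cannot appear in the data, while someone who survives to register brings a stretch of follow-up in which death could not have been observed. If that stretch counts as time at risk, early risk sets are too large and the early death rate is too low. Consecutive enrolment and the screening log (3.1 and 6.1) do not help, because neither can register a patient who has already died.

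Survival is among the treatment outcomes of the primary objective (2.1), and section 2.2 plans new prognostic scores. This version also adds higher-risk disease and AML with 20-30% blasts (1.4), with a target of at least 1000 higher-risk cases (3.2.1). Those are the patients in whom deaths within 100 days are most frequent. A larger sample does not reduce the error.

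**Working it through.** The protocol gives no survival estimate to reproduce, so the check asks how far an analysis with everyone at risk from day 0 would miss a known truth.

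**Inputs from the protocol**
- Longest delay: 100 days, D = 100/30.4375 = 3.285 months (3.1, 3.2.2).
- Survival in advanced disease: "Median survival of these patients is generally shorter than 12 months" (1.2). Medians of 12 and 9 months are used.

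**Assumptions not in the protocol**
- Exponential survival.
- Three delay patterns: all at day 30, uniform over 0-100 days, all at day 100.
- Medians of 24 and 60 months for better-prognosis disease.
- Delay unrelated to prognosis.

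**Formulas.** With median m, the rate is λ = ln 2/m. Let P be the probability of being alive at entry.
- Fixed delay d: P = exp(−λd).
- Uniform delay: P = (1 − exp(−λD))/(λD).
- Unadjusted survival for t ≥ D: S(t)/P.
- Unadjusted median: m + (−ln P)/λ.

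**Median 12 months.** λ = 0.05776, λD = 0.1898, S(12) = 50.0%.
- Day 30: P = exp(−0.0569) = 0.9447; survival 0.500/0.9447 = 52.9%; median 13.0 months.
- Uniform: P = (1 − 0.8271)/0.1898 = 0.911, so 8.9% die before entry; survival 54.9%; median 13.6 months.
- Day 100: P = 0.8271, so 17.3% are lost; survival 60.4%; median 15.3 months.

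**Median 60 months, uniform.** λD = 0.03795; P = 0.03724/0.03795 = 0.9813; 12-month survival 87.1% becomes 88.7%, an error of about 1.7 points before rounding.

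12-month survival by the same formulas:

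| Assumed median | True | All at day 30 | Uniform 0-100 d | All at day 100 |
|---|---|---|---|---|
| 9 months | 39.7% | 42.8% | 44.9% | 51.1% |
| 12 months | 50.0% | 52.9% | 54.9% | 60.4% |
| 24 months | 70.7% | 72.8% | 74.1% | 77.7% |
| 60 months | 87.1% | 88.1% | 88.7% | 90.4% |

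A simulation of 1,000,000 patients per scenario agrees to within about 0.1 point.

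**Does delayed entry repair it?** With uniform entry and a 12-month median, Kaplan-Meier with entry at inclusion returns 12.0 months and 50.0%. If everyone enters at the same day it cannot: at day 100 it still returns 15.3 months and about 60%. Only survival conditional on reaching that day can then be estimated.

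**Hazard ratios.** With the same fixed delay for all, every observed death falls after everyone has entered, so the Cox risk sets are already correct. Unadjusted Cox models on about 16,000 simulated patients gave 4.84 to 4.98 for a true ratio of 5.0 (medians 12 against 60) and 1.97 to 2.07 for a true ratio of 2.0 (12 against 24). A check with 1,000,000 per group, under uniform and day-100 entry, gave 5.01 and 4.99, and 2.00 in both cases. The absolute gap does narrow: with uniform entry the 12-month difference goes from 87.1 − 50.0 = 37.1 points to 88.7 − 54.9 = 33.8 points.

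**The case against.** The strongest reply is that section 5.3 only sets a time origin, which is the right one to keep. Kaplan-Meier and Cox both accept entry times, section 5 leaves details to a separate statistical analysis plan, and the study is exploratory (5.1). It is true that the plan could add delayed entry. But the protocol fixes the origin, the population and the estimators, and the usual reading of those three together gives a wrong early-survival figure. Nothing in the text prompts the correction.

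The objections on size also stand. The delay distribution is unknown. The figure of under 12 months in section 1.2 describes advanced disease under the FAB scheme, not the whole higher-risk group. The day-100 result is a bound.

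A reader might infer three stronger points that the protocol does not support:
- **That sub-studies on patients already included are restricted to survivors who re-consent.** Section 3.3.1.1 says only "patients (if (re-)consent is adequate" and accepts stored material from near diagnosis, so existing consent may suffice. The similar condition on national-registry uploads (6.1) does not say that a new consent is always needed.
- **That comparisons between risk groups or centres are distorted.** Hazard ratios hardly move under equal delay, and nothing shows that delay differs between groups.
- **That time to progression is inflated in the same way.** The interval before inclusion is not progression-free by construction. A progression in that window may still be recorded in a patient who registers by day 100.

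**Conclusion.** The point holds for absolute overall survival. Applied with everyone at risk from day 0, section 5.3 overstates early survival; the direction follows from the protocol's own entry and consent rules. With a 12-month median, the error at 12 months is about 3 points (entry at day 30), 5 points (uniform) and at most 10 points (all at day 100), and the median is 1.0 to 3.3 months too long. With a 60-month median and uniform entry it is about 1.7 points. These sizes rest on exponential survival and assumed delays; actual delays concentrated in the first weeks would make them smaller. Prognostic hazard ratios are little affected if delay is similar across groups. For progression the size is uncertain, and for re-consent an effect arises only where inclusion truly depended on being alive to give a new consent or sample.

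**What to change.** Amend section 5.3 as follows.

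1. **Overall survival.** Keep diagnosis as time zero, but have each patient enter the risk set at the date of inclusion in Kaplan-Meier and Cox analyses.
2. **Delay.** Report the distribution of diagnosis-to-inclusion time by risk group.
3. **Sparse early entry.** Where few patients enter early, report survival conditional on a landmark such as day 100.
4. **Progression.** Use the same entry time, and report progressions dated before inclusion separately, so that they are not dropped silently.
5. **Sub-studies.** Use a later entry date only for patients whose data or sample could be included solely because they were alive to give a new consent or sample.

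**Cost.** One entry-time argument in the survival code, using dates already collected; data collection and conduct do not change. Early intervals become slightly wider and survival slightly less favourable. The method assumes that entry time is independent of prognosis given the covariates, and this should be stated.
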